Concomitant Medications: All subjects will be asked about concomitant medications weekly during the lead-in and outpatient treatment period. Concomitant medications include both OTC and prescribed medications.

Early Life Stress Questionnaire (ELSQ): The Early Life Stress Questionnaire (McFarlane, Clark et al. 2005) (ELSQ) is a self-report questionnaire that considers 19 adverse life events (crime, sexual abuse, family conflict, bullying, etc.). High ELS is defined as exposure to ≥ 3 ELS events prior to age 19 (Cohen, Paul et al. 2006, Paul, Henry et al. 2008, Seckfort, Paul et al. 2008, Clark, Cohen et al. 2012), consistent with the rates of ELS in the general population (Cohen, Paul et al. 2006). Previous studies (Cohen, Grieve et al. 2006, Cohen, Paul et al. 2006, Seckfort, Paul et al. 2008, Clark, Cohen et al. 2012) have shown that using a cut-point of ≥ 3 ELS events provides the greatest discrimination on the basis of ELS for behavioral and neural measures. The ELSQ will be administered during week 3.

Perceived Stress Scale (PSS-14): The PSS-14 is a validated, self-report questionnaire that assesses the extent to which individuals perceive their life to be stressful (Cohen and Williamson 1988). The PSS-14 will be administered during baseline.

Posttraumatic Stress Disorder Checklist - Civilian version (PLC-C): is the most commonly used self-report questionnaire assessing number and severity of PTSD symptoms. The PLC-C will be administered during week 3.

Genotyping/SNP: 10 ml whole blood will be collected at baseline for DNA extraction for genotyping analyses.

Hamilton Depression Rating Scale (HAMD) (Riskind, Beck et al. 1987): Completed in just 5 to 10 minutes, the HAMD can be used to quickly evaluate symptom severity, to confirm a diagnosis of depression, to explore depressive symptoms, and to measure treatment outcome. The HAMD will be administered during the lead-in period and weekly during the medication and follow-up phase.

HIV CD4 Count and Viral Load: Participants who are HIV+ will have CD4 count and viral load measured at baseline, at the termination of medication (week 13), and at the last follow-up visit (week 16).

HIV medication adherence: Participants who are HIV positive will have their HIV medication adherence assessed monthly by asking them to estimate the proportion of their medications that they took in the past month.

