Hypothesis 3: IBUD will result in greater improvements in CD4 count, HIV viral load, and neurocognitive functioning than placebo among HIV positive participants.

Analysis: Change scores for CD4 count, HIV viral load, and scores on neurocognitive assessments will be calculated between baseline and end of medication treatment. The mean change score for each measure will be calculated for IBUD versus placebo. A linear regression model will be used to assess the mean change in measures for IBUD versus placebo after controlling for possible confounders such as gender, MA abstinence during the two-week lead-in period, and medication adherence.

Aim 4: To determine whether IBUD improves behavioral outcomes (sexual transmission behaviors; uptake and/or adherence to HIV medications) relative to placebo among HIV-positive MA dependent participants.

Hypothesis 4: IBUD will result in greater reductions in HIV risk behaviors and increased HIV medication uptake/adherence than placebo among HIV positive participants.

Analysis: The proportion of participants reporting HIV sexual risk behaviors in the IBUD and placebo groups will be calculated. The proportion of participants reporting receipt of HIV medications as well as the proportion of medication they report taking will be calculated. The mean number of self-reported HIV

[figure not shown]
sexual risk behaviors for IBUD versus placebo will be compared via t tests and then in a linear regression model controlling for potential confounders. The mean HIV medication adherence rate (proportion of medication taken) for IBUD and placebo will also be compared via t test and then linear regression model.

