Exploratory analyses Baseline neurocognitive functioning of participants will be described using results of the neuropsychiatric (NP) battery performed at baseline. Baseline to post-treatment changes in scores on tests in the NP battery will be calculated for IBUD and placebo groups. Effect sizes for IBUD on NP battery change scores will be calculated and used to determine whether future fully powered studies examining NP changes with IBUD are warranted. In addition, GEE models will be used to compare change in the brief serial weekly cognitive assessments (Balloon Analog Reaction Time task and Stop Signal test) during treatment with IBUD versus placebo. To explore whether severity/type of neurocognitive dysfunction at treatment entry mediates response to IBUD, baseline scores on NP assessments will be included as co-variables in the models assessing IBUD effects on MA use outcomes and treatment retention. Finally, potential effects of polymorphisms in dopaminergic genes and GDNF (Yoshimura, Usui et al. 2011), as well levels of inflammatory biomarkers and neurotrophic factors on treatment outcomes will be explored. The sample will be stratified by genotype for each SNP and changes in MA use and retention for IBUD versus placebo will be compared in these sub-groups. In addition, baseline versus post-treatment serum and plasma levels of inflammatory markers neurotrophic factors will be compared for IBUD versus placebo groups and by HIV serostatus. Correlation between early life stress measures and baseline severity of MA abuse as well as treatment outcomes, including potential early life stress-ibudilast interactions, will also be explored.

We recognize that the study is not powered to detect statistical significance in these analyses, especially if corrections for multiple testing are employed (Benjamini and Hochberg 1995) and as a result these analyses are by design for exploratory purposes only. Still we feel that including these probes of potential IBUD mechanisms of action within the context of this early clinical trial is important in that the results may bolster any observed effects of IBUD on MA use outcomes and direct the design of subsequent adequately powered confirmatory phase III trials.

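### Aims 3 and 4 name neither the outcome's own baseline as a covariate nor a scale for viral load; specifying both is a free gain in precision for exploratory analyses

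*Combined protocol and SAP*

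**What the plan says.** All references are to the combined protocol and SAP.

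**Data Analysis, Aim 3** covers CD4 count, viral load and neurocognitive scores in HIV-positive participants. "Change scores for CD4 count, HIV viral load, and scores on neurocognitive assessments will be calculated between baseline and end of medication treatment". Then "The mean change score for each measure will be calculated for IBUD versus placebo", followed by a linear regression of change on arm "after controlling for possible confounders such as gender, MA abstinence during the two-week lead-in period, and medication adherence". The baseline value of the outcome is not among the named covariates. No unit, transformation or rule for values below quantification is given for viral load.

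**Data Analysis, Aim 4** states the hypothesis that "IBUD will result in greater reductions in HIV risk behaviors and increased HIV medication uptake/adherence than placebo among HIV positive participants". The analysis text compares levels: the mean number of "sexual risk behaviors for IBUD versus placebo will be compared via t tests and then in a linear regression model controlling for potential confounders"; and "The mean HIV medication adherence rate (proportion of medication taken) for IBUD and placebo will also be compared via t test and then linear regression". Neither sentence names a time point or a baseline value.

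**Exploratory analyses** use the same change-score form for the cognitive battery: "Baseline to post-treatment changes in scores on tests in the NP battery will be calculated for IBUD and placebo groups". The resulting effect sizes are to inform whether larger studies are worth doing.

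**The baselines exist.** Under Study Measures and Assessments, "Participants who are HIV+ will have CD4 count and viral load measured at baseline", and again at weeks 13 and 16. The HIV risk scale is given at screening and monthly. Appendix II marks a baseline assessment for the risk scale, for HIV-medication adherence and for the repeated cognitive tests, apart from the Connors' CPT.

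**The concern.** When an outcome is measured before and after treatment in a randomised trial, adjusting the follow-up value for its own baseline is at least as precise as analysing change or follow-up alone. Aims 1 and 2 of the same section name baseline MA use as a covariate; Aims 3 and 4 name no equivalent for their own outcomes. Randomisation is stratified by HIV status, and the urn balances a MoCA split but not CD4 count or viral load, so chance imbalance in those two is left to the analysis.

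Viral load raises a separate question. Enrolment requires neither HIV treatment nor viral suppression, and Aim 4 studies uptake of HIV medication, so a mix of suppressed and viraemic participants is plausible. On an untransformed scale, a few large values would then drive the mean change.

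HIV-positive enrolment is capped at 70, and the Research Plan says these results may guide later development. Such a small subsample has little precision to spare. Leaving covariates and scale open also lets the model be chosen with the data in hand.

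**Working it through.** The plan gives no sample size, power, SD or correlation for Aims 3 and 4, so there is no stated figure to reproduce.

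**Inputs from the document:** at most 70 HIV-positive participants, taken as 35 per arm. This is a ceiling before attrition. The cognitive battery stopped after 85 randomised participants of either serostatus, which limits that outcome further.

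**Assumed inputs:** baseline to follow-up correlation r of 0.5 to 0.7; equal variance at both times; two-sided 0.05 (no level is stated for these aims); for viral load, a log-normal distribution with mean 4.0 log10, SD 0.8 to 1.0, r of 0.5 or 0.8, and a true effect of 0.5 log10.

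**Step 1: information lost.** In units of the outcome variance, the variance behind the arm contrast is 2(1 − r) for change, 1 for follow-up only, and 1 − r² for ANCOVA.

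- Loss from change = 1 − (1 − r²)/[2(1 − r)] = (1 − r)/2.
- Loss from follow-up only = r².

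| r | Change | Follow-up only | ANCOVA | Loss, change | Loss, follow-up only |
|---|---|---|---|---|---|
| 0.5 | 1.00 | 1 | 0.75 | 25% | 25% |
| 0.7 | 0.60 | 1 | 0.51 | 15% | 49% |

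Outside that range, the losses are 35% and 9% at r = 0.3, and 10% and 64% at r = 0.8. The change-score loss cannot exceed 50% for r ≥ 0. The follow-up-only loss passes 50% only when r exceeds about 0.71.

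**Step 2: detectable difference** at 80% power, in SD units: (1.96 + 0.84) × √(2/35 × variance).

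- r = 0.5: change 0.67, follow-up only 0.67, ANCOVA 0.58.
- r = 0.7: change 0.52, follow-up only 0.67, ANCOVA 0.48.

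**Step 3: viral load.** Power from 4,000 simulated trials per row:

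| log10 SD | r | Raw change | Raw ANCOVA | log10 change | log10 ANCOVA |
|---|---|---|---|---|---|
| 0.8 | 0.5 | 14.5% | 31.4% | 73.5% | 84.5% |
| 0.8 | 0.8 | 22.9% | 49.1% | 98.5% | 99.0% |
| 1.0 | 0.5 | 6.4% | 14.2% | 54.7% | 64.8% |
| 1.0 | 0.8 | 10.9% | 23.2% | 90.0% | 92.2% |

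Moving from raw change to log10 change adds roughly 48 to 79 percentage points. Adding the baseline then adds about 0.5 to 11. The gain is mostly the scale.

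**Sensitivity.** With less skew (SD 0.5), raw change reaches 52% at r = 0.5 and 75% at r = 0.8, against more than 99% for log10 ANCOVA. With many values at a floor (mean 2.5, SD 1.2, r = 0.7, floor at 50 copies), the figures are 4% and 56%. The direction holds throughout; the size depends on a distribution that the document does not give.

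**The case against.** The strongest reply is that the text is silent rather than wrong. The Aim 3 covariates are introduced as examples, Aim 4 refers to unnamed confounders for risk behaviour, and the opening of Data Analysis allows multivariable models where appropriate. Nothing excludes a baseline term or a log scale. That stands: the supportable statement is that these items are not specified. It does not remove the point, because an open list is not a pre-specified model, and the plan does name baseline use for Aims 1 and 2.

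Three stronger readings are tempting and should be resisted.

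- A reader might infer that viral load will be analysed as a raw difference in copies. No scale is stated, so the raw-scale power figures are conditional.
- A reader might infer that Aim 4 compares follow-up values alone. The analysis sentences fit that, but no time point is given and the hypothesis speaks of reductions.
- A reader might infer that most of the information in these aims is thrown away. For CD4 and cognitive change scores the loss is 15–25% in the assumed range and never above half for r ≥ 0. Only untransformed, skewed viral load could lose that much in Aim 3, and only a follow-up-only analysis with r above about 0.71 in Aim 4.

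It is also fair that Aims 3 and 4 are labelled exploratory, that the HIV-positive subsample is declared unpowered, and that randomisation keeps the change and follow-up comparisons unbiased, missing data aside. This lowers the severity. It does not make precision irrelevant, since the estimates are meant to guide later studies. The protection also does not extend to a model that conditions on medication adherence, which is observed after randomisation.

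**Conclusion.** The point holds as a minor, cost-free improvement. Aims 3 and 4 do not pre-specify adjustment for baselines that the trial collects, the scale of viral load, or the Aim 4 time point.

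The cost is precision, not validity of the randomised comparison. It is modest for CD4 and cognitive scores, and modest to substantial for Aim 4 if only follow-up is compared. It could be large for viral load if the data are skewed and left untransformed. These sizes rest on the assumed correlations, distribution and effect, and on 35 per arm as a best case. The primary outcome, its sample size and the safety monitoring are unaffected.

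**What to change.** Amend the Data Analysis text as follows.

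- **Aim 3 and the cognitive change scores under Exploratory analyses:** model the end-of-treatment value on arm plus its own baseline, with gender and lead-in abstinence. Keeping change as the response and adding the baseline value as a covariate gives the same arm effect, so the edit can be one phrase. Leave medication adherence out of the main model; it may be kept as a labelled secondary analysis.
- **Viral load:** analyse on the log10 scale and state in advance how values below quantification are handled. Which convention to use is for the trial team.
- **Aim 4:** name the end-of-treatment assessment to be used (Appendix II schedules both measures at week 12) and add the baseline risk-behaviour and HIV-medication-adherence values as covariates, with a rule for participants not on HIV medication at baseline. A count model for risk behaviour is an option, not a requirement.

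The cost is wording only, ideally before unblinding. No new data, visits or participants are needed.

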Examination of potential confounders Rates of adverse events and medication adherence in the IBUD and placebo groups will be calculated and compared. Medication adherence will be assessed as a continuous variable: the proportion of twice-weekly urine drug samples positive for riboflavin (≥ 900 ng/ml riboflavin as determined via quantitative fluorimetry), and as a dichotomous variable: medication adherent ($\geq 80\%$ of twice-weekly urine drug screens positive for riboflavin). Adherence will also be assessed via qualitative measurement of IBUD and metabolites in urine and serum samples, which is the gold standard for assessing adherence in the IBUD group but is limited by the fact that assessment of adherence in the placebo group is not possible. Models for MA use outcomes will be repeated including the continuous measure of adherence as a co-variate. The models will also be run with the sample stratified as medication adherent versus non-adherent. As pre-treatment abstinence is an important predictor of treatment outcomes and medication response in stimulant dependence trials (Elkashef, Rawson et al. 2008, Bisaga, Aharonovich et al. 2010), the sample will be stratified by ability to achieve initial abstinence with CM during the two-week lead-in period to explore whether medication effects may differ in these subgroups.

Aim 2: To determine whether IBUD results in longer treatment retention than placebo among MA dependent participants.

Hypothesis 2: IBUD will result in significantly greater treatment retention than placebo

Analysis: The mean number of days retained, defined as the number of days from the start of study medication to the final clinic visit during the 12 week treatment period, will be compared for IBUD versus placebo via t-test. Cox proportional hazards model will be used to compare days retained for IBUD versus placebo controlling for co-variables including age, gender, and baseline MA use. These analyses will then be repeated with the sample stratified by ability to achieve initial abstinence with CM during the two-week lead-in period to explore whether medication effects may differ in these subgroups.

The following exploratory HIV-related aims will be address in the HIV positive participants.

Aim 3: To determine whether IBUD improves biological (CD4 count; HIV RNA) and neurocognitive outcomes more than placebo among HIV-positive MA dependent participants.

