APPENDIX II: Assessment Schedule for Ibudilast Phase 2 Trial

STUDY ASSESSMENT TABLE FOR IBUDILAST PHASE II TRIAL

Measures	Baseline	Medication Phase			Follow-Up
		Weekly Wks 1-12	Specific time	Monthly Wk 4, 8, 12	
	0.6 visits				Weekly Wk 13, 14, 15, 16
Clinical measures					
Medical history	X				
Physical	X				wk 13
EKG	X		wks 3, 8		wk 13
Labs	X		wks 3, 8		wk 13
HCV serology	X				wk 13
HIV test	X				wk 13
if HIV+, CD4/viral load	X				wks 13, 16
DNA/SNP sample	X				
Inf/NT markers (serum and plasma)	X		wks 3, 8		wk 13
Pregnancy test	X			X	
Adverse events	X	X			X
Urine drug screen	e	e			X
Vital signs	e	e			X
Progress note	e	e			X
Urinary cotinine	X	X			X
Concomitant medications	X	X			
Pill count		X			wk 13
HIV medication adherence	X			X	wk 16
Medication compliance (urine) via UV fluorimetry	e	e			wk 13
Stored urine aliquot	X	e			
Medication compliance (serum)			wk 3		
Behavioral assessments					
ASI	X				
BIS-11	X				
PSS-14	X				
ELSQ			wk 3		
PLC-C			wk 3		
SCID	X				
WURS	X				
HRBS	X			X	wk 16
BSI	X			X	wk 16
MA Craving VAS	X	X			X
C-SSRS	X	X			X
HAMD	X	X			X
TLFB	X (0.1, 0.4)	X			X
Medical Management Counseling	X	X			
Cognitive functioning measures After July 2016, only MOCA is still being administered					
WTAR	X				
WRAT4	X				
MOCA	X (0.1)		wk 4		wk 13
BVMT-R	X		wk 4		wk 13
HVLT-R	X		wk 4		wk 13
CPT-II (MATRICS version)	X		wk 4		wk 13
CPT-II (Connors' version)			wks 2, 6, 10		
TMT	X		wk 4		wk 13
SST (comp)	X		wk 4		wk 13
DDT (comp)	X		wk 4		wk 13
Iowa Gambling Task	X		wk 4		wk 13
Symbol Coding (WAIS-IV)	X		wk 4		wk 13
Symbol Search (WAIS-IV)	X		wk 4		wk 13
Letter Number Sequencing (WAIS-IV)	X		wk 4		wk 13
N-Back Task	X		wk 4		wk 13
DKEFS Color Word Interference	X		wk 4		wk 13
Pursuit Rotor Task	X		wk 4		wk 13

e: every visit.

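### Aim 4 measures HIV-medication uptake without using baseline treatment status and, on its natural reading, compares adherence in a group formed after randomisation

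*Combined protocol and SAP*

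**What the plan says.** Under Data Analysis, the HIV aims are introduced with "The following exploratory HIV-related aims will be address in the HIV positive participants". Hypothesis 4 joins two outcomes in one directional statement: "increased HIV medication uptake/adherence than placebo among HIV positive participants".

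The Aim 4 analysis states: "The proportion of participants reporting receipt of HIV medications as well as the proportion of medication they report taking will be calculated". For adherence it adds: "The mean HIV medication adherence rate (proportion of medication taken) for IBUD and placebo will also be compared via t test", followed by a linear regression. The Aim 4 text names no between-arm comparison for receipt. The general strategy at the start of Data Analysis would supply a chi-square test by default.

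Under Study Measures and Assessments, HIV-positive participants report adherence monthly, by "asking them to estimate the proportion of their medications that they took in the past month". Appendix II also schedules the item "HIV medication adherence" at baseline and week 16. Prescribed concomitant medications are recorded weekly through lead-in and treatment.

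The plan is silent on two things. Nothing separates participants already on HIV medication at baseline from those who are not, and baseline HIV treatment is not among the covariates listed in Data Analysis. Nothing says whether a participant with no HIV medication is excluded from the adherence mean, treated as missing, or scored zero.

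**The concern.** Receipt during follow-up is a prevalence. Participants already treated at baseline cannot take up treatment, yet they count in both numerator and denominator. A real effect on starting is therefore shrunk. Part of any observed difference may also reflect how many in each arm were already treated. Under Randomization Procedures, allocation is stratified by HIV serostatus, and the urn balances lead-in abstinence, gender, ethnicity, marijuana dependence and MoCA score. HIV treatment is not among these.

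The adherence question has no answer for someone with no HIV medication. Unless the plan says otherwise, such people fall out of the mean. The arms are then compared in a group that exists only after randomisation and that depends partly on uptake, the other half of Hypothesis 4. The two halves of the outcome could then point in different directions for reasons unrelated to any individual's adherence.

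**Working it through.** The plan gives no rate, effect size or power for Aim 4, so there is no figure to reproduce. The check is mixture arithmetic.

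**Inputs.** From the documents: up to 70 HIV-positive participants, hence at most about 35 per arm. Assumed, because the documents are silent:
- share already treated at baseline, s, varied from 0 to 0.8, all of whom stay on treatment;
- probability of starting among the rest, p₀ = 0.20 on placebo and p₁ = 0.50 on IBUD;
- adherence of established takers, a = 0.90;
- adherence of new starters, b, varied from 0.50 to 0.95.

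**Step 1: dilution of uptake.** Receipt in an arm is s + (1−s)p, so the difference is (1−s)(p₁−p₀). At s = 0.7 this is 0.3 × 0.30 = 0.09. Power is by normal approximation, two-sided 0.05, and is rough for the smallest groups.

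| s | Receipt, placebo vs IBUD | Difference | Power, 35 per arm | Not treated at baseline, about n per arm | Power for the undiluted 0.30 |
|---|---|---|---|---|---|
| 0 | 0.20 vs 0.50 | 0.30 | 0.76 | 35 | 0.76 |
| 0.3 | 0.44 vs 0.65 | 0.21 | 0.42 | 24 | 0.59 |
| 0.5 | 0.60 vs 0.75 | 0.15 | 0.27 | 18 | 0.47 |
| 0.7 | 0.76 vs 0.85 | 0.09 | 0.16 | 11 | 0.31 |
| 0.8 | 0.84 vs 0.90 | 0.06 | 0.11 | 7 | 0.21 |

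Once anyone is already treated, the smaller baseline-defined group gives more power than the whole group, though both are low.

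**Step 2: chance imbalance.** With baseline HIV treatment unbalanced by design, the standard deviation of the between-arm difference in s is √(2s(1−s)/35). This is 0.120 at s = 0.5, 0.110 at s = 0.7 and 0.096 at s = 0.8. An imbalance d moves the receipt difference by d(1−p). At s = 0.8 one standard deviation moves it by 0.096 × 0.5 = 0.048 to 0.096 × 0.8 = 0.077, against an effect of 0.06. This is noise rather than bias, but baseline status would remove it.

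**Step 3: adherence among takers.** Mean adherence among those on medication is [sa + (1−s)pb] / [s + (1−s)p]. At s = 0.7 and b = 0.50:
- placebo: (0.63 + 0.03)/0.76 = 0.868;
- IBUD: (0.63 + 0.075)/0.85 = 0.829;
- difference: −0.039.

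Scoring non-takers as zero gives sa + (1−s)pb: 0.660 vs 0.705, a difference of +0.045. IBUD minus placebo over the range:

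| s | Analysis | b = 0.50 | b = 0.70 | b = 0.90 | b = 0.95 |
|---|---|---|---|---|---|
| 0.5 | takers only | −0.067 | −0.033 | 0 | +0.008 |
| 0.5 | non-takers scored 0 | +0.075 | +0.105 | +0.135 | +0.142 |
| 0.7 | takers only | −0.039 | −0.020 | 0 | +0.005 |
| 0.7 | non-takers scored 0 | +0.045 | +0.063 | +0.081 | +0.085 |
| 0.8 | takers only | −0.025 | −0.013 | 0 | +0.003 |
| 0.8 | non-takers scored 0 | +0.030 | +0.042 | +0.054 | +0.057 |

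Here a and b are the same in both arms, so no one's own adherence is altered by IBUD. The negative differences come entirely from who is in the mean. Restricting to participants on medication at baseline gives a − a = 0, the correct answer for them in this set-up.

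**The case against.** The plan never states that adherence is restricted to takers. It asks HIV-positive participants for the proportion taken and leaves the denominator open; if non-takers score zero, no case run shows a reversal. That stands: takers-only is the natural reading, not a stated rule.

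A reversal also needs new starters to adhere less than established takers, which the documents do not support. That stands too, and the result is conditional on it.

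Receipt among all HIV-positive participants is a valid randomised comparison. Dilution shrinks it without changing its expected sign, and it registers people who stop treatment, which a count of starts alone would miss. This stands as a reason to keep receipt as a supporting description. It does not make receipt a good measure of uptake.

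Scoring non-receipt as zero blends uptake into adherence, so that version belongs in a sensitivity analysis.

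Finally, the aim is exploratory and the plan disclaims power in the HIV-positive subsample. Even a sharp result would settle little: 1 of 7 against 4 of 7 starting has a two-sided Fisher p of about 0.27. This limits the weight of the point. Low power excuses a wide interval, but not an outcome whose sign can depend on an unstated choice.

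**Conclusion.** The concern holds in two parts of different strength.

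The uptake part is firm. Baseline treatment status is not used, and the contrast shrinks by the factor (1 − share already treated): an assumed 30 points becomes 15, 9 or 6 at 50%, 70% or 80% already treated. Its actual size is unknown because the documents give no baseline treatment share.

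The adherence part is conditional. On the natural reading the comparison group is formed after randomisation. With starters at 50% to 70% adherence against 90% for established takers, the difference is −1.3 to −6.7 points for 50% to 80% already treated. With equal adherence it is zero.

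A reader might infer that the plan restricts adherence to takers, that Aim 4 as a whole would point the wrong way, or that new starters enter the mean in one arm only. The documents support none of these. The denominator is unspecified, receipt keeps the right expected sign and is reported beside adherence, and starters can enter both arms, in different numbers if IBUD changes uptake.

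The change is worth making because it is cheap. The primary outcome is unaffected.

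**What to change.** Amend the Aim 4 analysis text, using data already scheduled:

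1. **Uptake.** Define it as starting HIV medication during weeks 1–12 among HIV-positive participants not receiving it at baseline. Name the between-arm comparison, for example a difference in proportions with a confidence interval and an exact test. Keep overall receipt as a supporting description, since it also captures stopping.
2. **Adherence.** Compare the arms among HIV-positive participants receiving medication at baseline, adjusting for baseline adherence and counting those who stop as 0%. State which monthly assessments are used, and keep a missed assessment distinct from stopping. Add an all-HIV-positive analysis scoring non-receipt as 0%, labelled as a sensitivity analysis that combines uptake with adherence.

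The cost is analysis wording only. Baseline status should be derivable from the baseline adherence item in Appendix II and the lead-in concomitant medication record. The drawback is that the uptake group may be small (about 7 per arm if 80% are already treated) and its interval wide, which is acceptable for an exploratory, unpowered aim.

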HIV Risk-taking Behavior Scale: This is a self-administered assessment of the subject's engagement in activities that increase the likelihood of contracting HIV (Darke et al, 1991). This measure will be administered at screening (McDonald and Calhoun 2010) and monthly during the medication phase.

MA Craving Visual Analog Scale (Griffiths et al., 1993): Craving is a complex biological and psychological phenomenon. Subjective effects will be measured using a visual analog scale that ranges from 0 (not at all) to 100 (extremely) assessing strongest craving in the past 24 hours, the ability to refuse MA, “want” of methamphetamine, use if access to drug, etc. This measure will be administered during screening and weekly during the medication and termination.

Medication compliance: As described above, aliquots (5 ml) from each twice weekly urine sample as well as a serum sample (10 ml) during week 3 of study medication will be collected for measurement of concentrations of IBUD and its primary metabolite as a marker of medication adherence.

Physical examination/medical and neurological history/labs/EKG: A medical history, neurological history, and physical exam with all participants during the screening period. An EKG, blood chemistry panel (including liver profile and GGT), HIV and hepatitis C virus serology, PPD (if not previously completed), CBC, and urinalysis will be completed during screening and at termination. Hematology and chemistry labs (including liver panel and GGT) and an EKG will be repeated during week 3 and week 8 of study medication as well as at termination (week 13) for safety monitoring purposes. Female participants will have a urine pregnancy test monthly.

Self-Report of Medication Adherence/Pill Count: Using a the participant's medication blister package as a visual aide, research staff will sit with each participant at each study visit and review study medication-taking in the period since the participant's last visit. All study medications drugs taken will be plotted on the pill count record and deviations from the prescribed dosage will be noted. Non-adherent subjects will review medication dosing procedures with a study clinician and barriers to compliance will be discussed.

Inflammatory and neurotrophic markers: Serum and plasma will be collected from whole blood during baseline and during weeks 3, 8 and 13 for assessment of these markers.

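### Aim 4 compares monthly risk-behaviour and HIV-medication adherence data by t-test and linear regression, naming no visit, baseline adjustment or repeated-measures model; a longitudinal model, fitted in all participants for the risk scale, would be a cheap improvement

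*Combined protocol and SAP*

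**What the plan says.** The Data Analysis section introduces Aims 3 and 4 with: "The following exploratory HIV-related aims will be address in the HIV positive participants". Aim 4 concerns sexual transmission behaviours and uptake and/or "adherence to HIV medications) relative to placebo among HIV-positive MA dependent participants". Hypothesis 4 predicts larger reductions in risk behaviour, and more uptake and adherence, on IBUD.

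The Aim 4 analysis has three parts:
- Proportions by arm are calculated for sexual risk behaviours and for receipt of HIV medication.
- The mean number of self-reported HIV "sexual risk behaviors for IBUD versus placebo will be compared via t tests and then in a linear regression model controlling for potential confounders".
- Mean HIV-medication adherence is compared by t-test and then linear regression.

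On data collection, Study Measures and Assessments describes the HIV Risk-taking Behavior Scale as covering "engagement in activities that increase the likelihood of contracting HIV". It is given at screening "and monthly during the medication phase", with no limit by HIV status. Appendix II lists it at baseline, weeks 4, 8 and 12, and week 16, again without a limit. Where a measure is for HIV-positive participants only, the document says so: Appendix II has "if HIV+, CD4/viral load", and Study Measures has "Participants who are HIV positive will have their HIV medication adherence assessed monthly".

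**The concern.** Hypothesis 4 is about change, and both outcomes are measured before treatment and three times during it. The stated comparison is of means. It does not say which visit or per-person summary is used, or whether baseline enters the model. Aim 3, immediately before it, does specify change from baseline to the end of medication. Elsewhere the plan names GEE for repeated MA-use data (Aim 1) and for the serial cognitive tests (Exploratory analyses), but not here.

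The risk scale raises a second issue. It is collected from everyone, and its description fits HIV-negative participants literally, but no named analysis uses their scores.

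At stake are precision for Aim 4, room to choose the visit after seeing the data, and an exploratory estimate that could be had from data already scheduled for collection.

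**Working it through.** **1. Collection against analysis**

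| Measure | Collected from | Scheduled (Appendix II) | Named analysis |
|---|---|---|---|
| Risk scale | All participants | Baseline, weeks 4, 8, 12, 16 | t-test, linear regression; HIV-positive only; no visit named |
| HIV-medication adherence | HIV-positive | Baseline, weeks 4, 8, 12, 16 | t-test, linear regression; no visit named |

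The Aim 4 text does not name its instrument. The risk scale is the only HIV-risk instrument in the schedule, so the link is a strong inference.

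**2. Numbers available**

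The Research Plan gives 140 randomised participants, stratified by HIV serostatus, with up to 70 HIV-positive. I take 35 per arm in the subset at the cap and 70 per arm overall. The plan states no alpha, effect size or power for Aim 4, so there is no figure to reproduce. It does say that the HIV-positive subsample is not powered.

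**3. Detectable difference**

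Assumptions not in the documents: two-sided 0.05, 80% power, equal arms, SD 1, no dropout, and equal within-person correlation ρ of 0.5-0.7 between visits.

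One visit: (1.960 + 0.842) × √(2/n)
- n = 35: 2.802 × 0.2390 = 0.670 SD
- n = 70: 2.802 × 0.1690 = 0.474 SD

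The mean of three visits has variance (1 + 2ρ)/3:
- ρ = 0.5: 0.667, square root 0.816
- ρ = 0.7: 0.800, square root 0.894

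Results:
- HIV-positive subset: 0.670 × 0.816 = 0.55 and 0.670 × 0.894 = 0.60 SD
- Overall effect in all 140: 0.474 × 0.816 = 0.39 and 0.474 × 0.894 = 0.42 SD

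Only the first line bears on Aim 4. If 40-50 HIV-positive participants enrol (20-25 per arm), the single-visit figure is 0.89-0.79 SD.

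**4. Baseline adjustment**

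The figures above count averaging only. If baseline has the same correlation ρ with each visit, adjusting for it subtracts ρ² from the variance. As an illustration, take ρ = 0.6, a true difference of 0.4 SD and 35 per arm:

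| Analysis | Variance | Power |
|---|---|---|
| One visit | 1 | 39% |
| Mean of three | (1 + 1.2)/3 = 0.733 | 50% |
| One visit, baseline-adjusted | 1 − 0.36 = 0.64 | 55% |
| Mean of three, baseline-adjusted | 0.733 − 0.36 = 0.373 | 78% |

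The planned regression might already include baseline among its confounders, but the text does not say so.

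**The case against.** Restricting Aim 4 to HIV-positive participants is deliberate. Transmission by infected people is a coherent question, Aims 3 and 4 are labelled exploratory, and the Research Plan concedes that the subset is not powered. Risk behaviour in HIV-negative participants is a different estimand. This stands: the restriction is not an error, and a full-sample result belongs beside Aim 4 rather than in its place.

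The opening of Data Analysis also promises bivariate tests across all outcome variables, and multivariate models that may control for HIV status. That could be read as reaching the risk scale. It does not name the scale, though, and it specifies no longitudinal model.

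A reader might go further in three ways that the documents do not support:
- **That a t-test must either discard visits or treat them as independent, inflating the false-positive rate.** A t-test on per-person means or change scores does neither and is valid. Nothing in the plan says that visits will be pooled as independent.
- **That most of the risk-scale data go unused.** This depends on a visit choice the plan does not state. Of 140 × 5 = 700 scheduled administrations, one visit in 70 HIV-positive participants uses 70 (10%) and a change score uses 140 (20%). Using all five occasions takes 350 (50%), which leaves exactly half.
- **That Aim 4 would improve from 0.67 to about 0.4 SD.** That compares the HIV-positive effect with the overall effect in all 140. With an arm-by-serostatus term, the HIV-positive estimate still rests on at most 35 per arm.

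**Conclusion.** The point holds as a cheap improvement. The plan names no visit, baseline adjustment or repeated-measures model for two outcomes that it measures at baseline and monthly, and it names no use of the risk scale in HIV-negative participants.

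For Aim 4 itself the gain from using three visits is modest: about 0.67 to 0.55-0.60 SD detectable with 80% power, at the cap of 35 per arm. It rests on assumed correlations of 0.5-0.7, two-sided 0.05 and no dropout. The protocol expects high attrition, which would shrink the gain. The 0.39-0.42 SD figure describes only an overall effect in all 140. For adherence the numbers may be smaller still, since the proportion taken is defined only for people on HIV medication. No conclusion on the primary outcome, retention or safety depends on this point.

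**What to change.** Replace the Aim 4 analysis text with a prespecified longitudinal model:

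1. Name the instrument and score used for sexual risk behaviour.
2. Model weeks 4, 8 and 12 with GEE or a mixed model, adjusted for the baseline value, using a count or ordinal link if the scores are skewed. State the treatment contrast, such as the average over the three visits, and the missing-data assumption.
3. For the risk scale, fit the model in all randomised participants with arm, visit, HIV serostatus (already a randomisation stratum) and arm-by-serostatus. Report the HIV-positive estimate as the Aim 4 result. Label the HIV-negative and overall estimates as additional exploratory results.
4. For HIV-medication adherence, use the same repeated-measures approach within the HIV-positive group.

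The cost is a paragraph of analysis plan, slightly more analysis work and one more exploratory comparison. No new data, visits or participants are needed.
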